The register contains the following data on drugs prescribed and dispensed in ambulatory care: dispensed item (substance, brand name, formulation, and package); dispensed amount, dosage, expenditure, and reimbursement; age, sex, and unique identifier (personal registration number) of the patient; place of residence of the patient (county, municipality, and parish); date of prescribing and dispensing; the practice (primary health care centre or hospital clinic) that issued the prescription; and the prescriber's profession (e.g., general practitioner; specialist in internal medicine, psychiatry, or paediatrics). All drugs are classified according to the ATC classification system. The register does not include data on over-the-counter (OTC) medications or drugs administered in hospitals or complete data on drugs that are used in ambulatory care but are administered during day care at hospitals. The register is not complete with regard to drugs used in nursing homes.

Italy

In Italy, data sources have limited reference population size or limited availability of variables relevant for the proposed study. Additionally, linaclotide sales in Italy started in September 2014 hence the sample size contributed by Italy is relatively small.

Proposed Database: Health Search/CSD Longitudinal Patient Database

Health Search was founded in 1998 as a research unit of the Italian College of General Practitioners (SIMG). SIMG is a scientific society aimed to promote the role of General Practice within the National Health System. The main activities are focused on education and research. Research is mainly developed throughout the Health Search network, based on: (1) a school in which PCPs receive training and share

the same standards for recording electronic patients' information; (2) a database (Health Search), where PCPs collect patients' information. The group working with HSD data is a multidisciplinary team of epidemiologists, statisticians and IT experts; it provides value-added services to: (1) the PCPs who contribute to the HSD; (2) the stakeholders that are interested in using this research tool. Health Search-SIMG is currently involved in several national and multinational research projects on drug safety and drug utilization, health technology assessment (HTA) and health services research studies.

The HSD collects longitudinal data from approximately 900 active GPs across Italy, with 700 of them selected as most reliable for research purposes. The HSD contains patient demographic information, medical data (e.g., diagnoses, tests and test results, hospitalization, etc.), drug prescription, and prevention information, collected when patients visit PCPs, from approximately 2.4 million patients, and one million active patients currently assisted by the GPs selected for research project participation. The current average length of patient's electronic medical records since inception of the database is approximately 10 years. A unique identification number links all data for an individual patient in an anonymous way and no identifying details are available. The geographical distribution of patients of these PCP is from 16 Italian regions and similar to the general Italian population, without significant differences both in geographical location and age distribution (Prezioso et al., 2014; Masclee et al., 2013). The latest data currently available for research is data up to 31 December 2013.

The proposed database has been used in previous studies that also included similar European population-based primary care databases such as CPRD (Masclee et al., 2013).

Alternative Data Source: Local Health Units

A Local Health Unit (LHU) is a body assigned by the National Health System in Italy to provide healthcare to a specific geographic area, generally a province. The LHUs in Italy are responsible for assessing the medical needs and providing comprehensive care for a defined population. Each LHU is responsible for the hospital and primary care services in its area as well as for prevention and health promotion activities. LHUs have an information network that measures the expenditure for drug reimbursement for registered patients. LHUs record all claims from pharmacies concerning drugs that are fully or partially reimbursed. The data available include: demographics, hospital admission and discharge diagnoses, specialist visits, drug prescription and dispensation (primary care only), mortality and costs. A patient's personal health number can be cross-checked with the registry office and hospital database. This allows the information to be connected to the date of birth, gender and any record of previous hospitalisations. Diagnoses and procedures are recorded based on the International Classification of Diseases (ICD)-9 and ICD-9-CM codes. On average, each LHU covers a total population of 500,000 beneficiaries, and 3 to 5 LHUs have been included by Evidera in previous studies. The main limitation of this database for our current study is its lack of primary care and specialist diagnosis records.

Alternative Data Source: Cegedim Longitudinal Patient Database

The CSD Medical Research group provides access to European longitudinal patient data using data collected from the electronic medical records entered into a primary care physician's software, including 700 GPs attending over 800,000 patients from Italy. CSD includes information on the patient profile, clinical profile, prescriptions and the prescriber profile, but no information on hospital admissions (date of admission, admission diagnosis, discharge diagnosis, hospital stay duration, accident and emergency (A&E) visits or discharge status). Data characteristics are similar to those in the proposed database.

Data Source Excluded: Friuli Venezia Giulia Regional Information Health System (FVG)

FVG is in the northeastern part of Italy and has approximately 1.2 million inhabitants. In Italy, all citizens are covered by taxed-based public health insurance. The hospital discharge database of the FVG region of Italy routinely collects data from all hospitals in the region and includes information on patients' sociodemographic characteristics and treatment received during hospitalization. Given that the LHUs can capture the same data, in a larger population, this database was excluded.

Pilot Study Summary Report

Background

AbbVie is planning a nested case-control study to assess the safety of linaclotide, authorised for the symptomatic treatment of moderate-to-severe irritable bowel syndrome predominantly with constipation (IBS-C) in adults. The study goal is to assess the risk of severe complications of diarrhoea (SCD) among patients with IBS-C exposed to linaclotide or other treatments, controlling for potential risk factors. This study will be conducted in the United Kingdom (UK), amongst other countries, using data from the Clinical Practice Research Datalink (CPRD).

Information on IBS-C and SCD is not well captured in electronic data sources by standard diagnosis codes, therefore, the study plan includes additional primary data collection from general practitioners (GPs) to validate IBS-C diagnoses and potential SCD events identified through an algorithm based on electronic records. This type of additional data collection is feasible in the UK with the use of the CPRD. For cases and controls (or a sample of them, depending on the number of cases and controls), validation data will be collected through a questionnaire mailed to the attending GP with whom each identified study subject is registered.

Before using the questionnaire to collect information about IBS-C diagnoses and potential SCD events in the safety study, we conducted a pilot study to test this questionnaire with a small number of physicians in the UK.

Objective and Rationale

The objective of the pilot study was to assess the face validity of a questionnaire to collect information from PCPs to validate:

1. The correct identification of the study population (cohort of patients with IBS-C)
2. The patients experiencing the endpoints of interest

Study Design

For the execution of the pilot study, we worked in collaboration with the CPRD. GPs from practices contributing into the CPRD were randomly selected among those practices with a good track record of collaboration on prior research and were invited to participate in this pilot study.

GPs were approached and requested to participate, providing feedback through two alternative means:

- In writing (draft questionnaires were sent to GPs to be filled out and returned to the CPRD before the answers were anonymously provided to Evidera). We planned to target 12 GPs in an effort to obtain six questionnaires back.
- Orally, through a telephone interview. The CPRD was in charge of obtaining the informed consent from GPs, providing to Evidera only their first name and telephone number before they were contacted and interviewed (no further information that could identify the GP or the practice they work on was shared or sought). Telephone interviews intended to collect suggestions to any parts of the questionnaire deemed unclear, to gather feedback on coding habits, and to provide the opportunity to ask questions to the GPs about the feedback just provided, for clarification of any heterogeneous interpretations of the questionnaire. We targeted four GPs for telephone interviews.

The target number of GPs participating in this pilot study was selected to balance feedback diversity and logistical considerations, such as resources needed and time to collect responses. Reminders were sent if no response was returned after two weeks from the GPs receiving the questionnaires.

The documentation sent to GPs included questions on the GPs' coding habits for patients with IBS-C in addition to the draft questionnaires intended for case (patients with IBS-C experiencing SCD) and control validation. GPs were asked about the order and wording of the questions, whether they were

user friendly and easily understandable, and any suggestions they might have to improve the questionnaire. Questions related to the proposed Read codes to define patients with IBS-C were aimed to help understand how GPs code patients with IBS-C, since there is no single, specific code for this condition.

An optional second phase was also planned, in case significant changes to the questionnaire were necessary as a result of the collected feedback during the first phase. This second phase would assess the feasibility of using the updated questionnaire to capture the required information for validation of the safety endpoints. For this, we planned that the CPRD would target GPs who had at least one patient with IBS-C, as defined by the study-proposed combination of Read code of IBS plus a Read code for constipation or constipation-related symptoms. If this phase was necessary, we would have targeted 12 additional GPs and asked them to fill the updated questionnaire on one IBS-C patient each. The answers to the questionnaires would have provided the expected information or otherwise suggest that the questionnaire was not well understood and had to be amended consequently.

Results

The pilot study was initiated in November 2014, and closed at the end of February 2015.

We eventually targeted 19 GPs for the written questionnaire and six for the telephone interview. These numbers were larger than originally planned in an attempt to increase the chances of response in a short period of time that included the holiday season, when we anticipated a low response rate.

Two weeks after the questionnaires were first distributed, a reminder was sent to all non-responding GPs. Two GPs agreed to participate in the telephone interview and interviews were conducted. Additionally, written questionnaires were completed by five GPs and returned.

The feedback received is summarized below:

- GP coding practices of patients with IBS-C

J521 codes were the preferred codes for GPs to indicate patients with IBS-C, and the code for 'IBS' (J521.11) was selected by all GPs except one. 'History of IBS' (14CF.00) was marked by one GP but also noted by another GP as a code that would not be used to identify a patient with IBS-C. The use of free text to identify patients with IBS-C was recommended.

19C codes were the preferred codes for constipation, ahead of J520 codes. 'Constipation symptom' (19C..11) and 'Constipation' (19C..00) were the preferred codes among the former, with 'Constipation – functional' (J520.00), and 'Constipation NOS' (J520z00) among the latter. 'Psychogenic constipation' (E264500) was reported as a code that would not be used in a patient with IBS-C.

Other constipation-related symptoms frequently used in patients with IBS-C included: 'Colicky abdominal pain' (1962.00), 'Abdominal pain' (1969.00), 'Generalised abdominal pain' (197A.00), 'Abdominal distension symptom' (19A..00), 'Bloating symptom' (19B..12) and 'Nausea' (198..00). Additional codes occasionally used included: 'Central abdominal pain' (1971.00), 'Epigastric pain' (1972.00), 'Lower abdominal pain' (197C.00), 'Abdominal discomfort' (1968.00), '[D] Bloating' (R073400), '[D] Flatulence, eructation and gas pain' (R073.00) and 'Nausea symptoms' (198..12). Working diagnoses codes (including '[D]') were not likely to be preferred to code patients with IBS-C, (chosen only by one GP).

- Face-validity of the questionnaire

It was confirmed that if diarrhoea is severe, a Read code for diarrhoea should be expected in the patient's electronic medical record (EMR).

The questions to validate the SCD were all understood without difficulties and no suggestions for changes to the questions were proposed. Responses from GPs were: "Seems quite straightforward", "All questions appear clear enough", "I am content with this questionnaire, it seems straight forward to me",

"All questions seem clear and reasonable except that there is no definition of diarrhea or constipation", and [No comment].

The only suggestion provided was to review the formatting of the questionnaire because some of the answers with tick boxes were misaligned in the copy received by the GP.

One of the interviewed GPs estimated that filling out the questionnaire could take between five and 20 minutes, depending on how long the patient history is.

Given no significant changes were recommended, the second phase of the pilot study was not conducted.

Conclusions

The results of the pilot study showed that the proposed questionnaire for validation of patients with SCD appears to be user-friendly to the responding GPs and straight forward to fill out. No significant suggestions for changes to the questionnaire were proposed. The optional second phase to this pilot study was not deemed necessary.

The pilot study also showed that in terms of coding practices, most GPs mentioned the combination of codes J521.11 "IBS" and 19C.11 "Constipation Symptom" or 19C..00 "Constipation" as the preferred one used to identify IBS-C cases. Additionally, the use of free text to identify patients with IBS-C was recommended.

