For each medication of interest, a patient (cases and controls) will be classified at the index date according to the following user experience (time window of exposure to the medication):

- Current user, if there was a prescription or dispensation of the medication of interest with supply until the index date or supply that ended in the 90 days before the index date.
- Non-current user, if the last prescription or dispensation was issued longer than 90 days before index date
- Never user, if there is no prescription or dispensation history for that medication.

The main exposures or potential risk factors of interest are:

- Linaclotide user experience category as described above
- Laxatives user experience category as described above

Additionally, other variables listed above will be included in the analyses. Duration of medication use for each of the medications of interest will also be used (defined as time since the first documented prescription without discontinuation until the case or control index date).

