9.9 LIMITATIONS OF THE RESEARCH METHODS

Categorisation of patients with IBS into IBS-C, IBS-D, or IBS-M might be challenging. Similarly, the classification into mild, moderate, and severe IBS-C is not recorded in the databases and is expected to be available only for a fraction of patients. Differentiation between IBS-C and chronic constipation will also be challenging. As a consequence, some degree of misclassification is to be expected.

In the databases, we may miss some occurrences of safety endpoints (e.g., electrolyte imbalance) if they are not explicitly recorded; however, this is expected to affect only patients with complications of diarrhoea of milder severity.

The use of over-the-counter medications for the treatment of IBS-C-related symptoms, constipation, and diarrhoea is acknowledged as another study limitation. We will include over-the-counter medications, such as laxatives, when this information is recorded in the databases and reported by PCPs answering the study validation questionnaire. However, we expect under-recording of over-the-counter medications in the databases, and therefore the overall use of laxatives will be incompletely reflected. If the extent of misclassification of laxative exposure is different among cases and controls then some of the odds ratios could be biased and this limitation should be taken into account when the results are interpreted.

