IBS-C Event Date: _____

Diarrhoea Episode Date: _____

We are conducting a post-authorisation safety study on drugs used for irritable bowel syndrome and predominantly constipation (IBS-C) in anonymised electronic database health records. For this purpose we would like to collect information strictly and only for the patient with the above mentioned ID number, who meets the study inclusion criteria. Please provide us with answers to the ten questions below reporting information from the medical history of the patient identified above:

Diagnosis Confirmation

1. The above patient has been identified as experiencing IBS-C approximately on [IBS-C event date]. Could you please either confirm or correct our information based on your most recent knowledge? Mark only one:

Yes, I confirm the IBS-C diagnosis

No, the IBS-C diagnosis is not confirmed, instead the gastrointestinal (GI) diagnosis is

(If the IBS diagnosis is not confirmed please skip to question 5, otherwise continue to question 2)

2. Which drug was the main treatment used on [IBS-C event date] for managing IBS-C?:

_____ Dose: _____

3. Please confirm the earliest date of prescription for that treatment: _____

4. Which other treatments did the patient use on [IBS-C event date] or the days prior, for the management of the IBS-C? (Please provide either active substance, brand name or both, as available)

a. _____ Dose: _____

b. _____ Dose: _____

c. _____ Dose: _____

Diarrhoea Occurrence

5. Records show that this patient experienced an episode of diarrhoea on the [diarrhoea episode date].

I confirm the diarrhoea diagnosis approximately on the above date Yes No

If the answer is No please skip to Question 10, otherwise continue to question 6

6. If this patient was on treatment for IBS-C, were any of the treatments above discontinued due to this diarrhoea episode?
- Yes, there were treatments for IBS-C that were discontinued
- No, the patient was not on treatment for IBS-C or the treatment(s) was(were) not discontinued
7. If Yes, please specify the name of the drug(s) discontinued and the response to discontinuation
- a. _____ diarrhoea improved stayed the same worsened
- b. _____ diarrhoea improved stayed the same worsened
- c. _____ diarrhoea improved stayed the same worsened
- d. _____ diarrhoea improved stayed the same worsened

Complications of Diarrhoea

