8. Did this diarrhoea episode require medical assistance or treatment other than soft diet, oral rehydration and the treatment discontinuation mentioned above, if any? Yes No
9. If you responded "Yes" to question 8, please mark all that apply from the following list, otherwise skip to Question 10.

The patient experienced ...

- dehydration that required intravenous rehydration (a)
- dehydration that required oral rehydration with solutions of electrolytes (b)
- serum potassium levels < 3.0 mEq/L (c)
- oliguria, defined a urine output < 400 mL in 24 hours (d)
- anuria, defined a urine output < 50 mL in 24 hours (e)
- serum potassium levels between 3.0 and 3.5 mEq/L (f)
- serum sodium levels > 150 mEq/L (g)
- new onset thromboembolism episodes (h)
- new onset orthostatic hypotension episodes (i)
- new onset syncope (j)
- new onset dizziness (k)
- new onset vertigo (l)
- acute renal failure (m)
- hypovolaemic shock (n)
- stupor (o)
- coma (p)
- The patient required hospitalisation because of the diarrhoea (q)
- The patient went to an emergency department or urgent care clinic due to the diarrhoea (r)
- The patient died shortly after the diarrhoea episodes (s)

- Patient's death was related to treatment for IBS (t)
- The patient restarted treatment for IBS after recovery from diarrhoea (u)
- Other treatment (v) (specify)

.....
.....

- Other laboratory outcomes (w) (specify)

.....
.....

Risk Factors for Complications

10. Did the patient have any of the following diagnosis on the [diarrhoea episode date]? (Please check all that apply):

- Hypertension (a) Diabetes (b) Cardiovascular disease (c)
- Crohn's disease (d) Ulcerative colitis (e) Microscopic colitis (f)
- Other risk factors for diarrhoea (g) (specify)

.....
.....

Thank you for your cooperation. For any questions regarding this research please contact us:

Name *Organisation* *Postal address* *Email address*

Database Feasibility Assessment

This section includes a summary of the databases assessed to be used for the linaclotide studies, planned to be implemented in the UK, Spain, and Sweden. All databases identified were explored for feasibility and data content, as well as interest in conducting and availability to conduct the studies. This section contains the information provided by the candidate data sources contacted for this purpose.

Database Identification

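### The UK physician questionnaire records treatment at the IBS-C event date, but laxative exposure is defined at the index date, and Section 9.9 plans to use the form's over-the-counter laxative answers

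*Protocol*

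**What the plan says.** The form in Annex 3 (Physician's Questionnaire) has two date fields, one for the IBS-C event and one for the diarrhoea episode. Question 2 asks "Which drug was the main treatment used on [IBS-C event date] for managing IBS-C". Question 4 asks "Which other treatments did the patient use on [IBS-C event date] or the days prior, for the management of the IBS-C". Question 3 asks only for the earliest prescription date of the main treatment. Question 6 turns to the diarrhoea but asks "were any of the treatments above discontinued due to this diarrhoea episode", and question 7 asks for the names of the stopped drugs and the response. Question 10 does use the diarrhoea date, but only for diagnoses: "Did the patient have any of the following diagnosis on the [diarrhoea episode date".

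Section 9.2.1.2 sets the case index date at the first diarrhoea episode that is followed by a listed outcome. Section 9.2.1.3 gives each control its case's index date. Under Section 9.3.2, for each medication of interest "a patient (cases and controls) will be classified at the index date according to the following user experience", and linaclotide and laxatives are named as the main exposures. Section 9.7.3.1 enters both into the model at the index date. Section 9.9 says over-the-counter medicines such as laxatives will be included when recorded in the databases "and reported by PCPs answering the study validation questionnaire".

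**The concern.** The only questions that elicit treatments refer to a different date from the one at which exposure is classified. If the answers are used as Section 9.9 says, a laxative taken around the time IBS-C was identified could be counted as laxative use at the index date. One started later could go unrecorded. This would affect UK patients with a returned form only, so laxative exposure would be measured differently in responders and in everyone else.

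The skip rules can also make collection uneven between cases and controls. Section 9.9 itself warns that laxative misclassification that differs between cases and controls could bias odds ratios. At stake is the laxative odds ratio and, because laxatives are also adjusted for, the quality of that adjustment in the linaclotide estimate.

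**Working it through.** **1. Time anchors, side by side**

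- Questions 2 and 4, the only treatment lists: IBS-C event date, with question 4 looking backward from it.
- Question 3: start of the main treatment. No item asks when use ended, apart from stopping because of the diarrhoea.
- Questions 6 and 7: the diarrhoea episode, but worded for the drugs already listed.
- Exposure in Sections 9.3.2 and 9.7.3.1: index date. Current use means supply up to that date or ending in the 90 days before it.
- Earlier in Section 9.3.2, medications including linaclotide and laxatives are defined by a prescription in the prior 45 days. The two windows differ.

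**2. Skips**

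- After question 1: "If the IBS diagnosis is not confirmed please skip to question 5, otherwise continue to question 2". Without a confirmed IBS-C diagnosis no treatment is listed.
- After question 5: "If the answer is No please skip to Question 10, otherwise continue to question 6". Without confirmed diarrhoea, questions 6 to 9 drop out, and with them the only treatment items tied to the episode. If controls receive the form printed in Annex 3, this falls mainly on them, because cases are selected for having diarrhoea.

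**3. Which exposures depend on the form**

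Section 9.7.2.1 takes exposure to linaclotide and to laxatives from database prescriptions. Nothing lets the form overwrite a linaclotide record. Over-the-counter laxatives are different, because Section 9.9 names the form as a source for them.

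**4. How far apart the dates can be**

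The IBS-C event date is not defined. Assume that it is the UK cohort entry date, which is 13 May 2013 at the earliest (Section 9.2.1.4). The last UK data date is 17 November 2023 (Table 1).

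- 13 May 2013 to 13 May 2023: 3,652 days
- 13 May 2023 to 17 November 2023: 188 days
- Total: 3,652 + 188 = 3,840 days, and 3,840 / 365.25 = 10.5 years

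This is the maximum under that assumption. If the date is instead the first IBS-C record of a prevalent patient, the gap can be longer. The protocol gives no distribution for it.

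**5. What wrongly dated answers could do (illustration, assumed values)**

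With true exposure prevalence p, sensitivity Se and specificity Sp, the observed prevalence is q = Se·p + (1 − Sp)(1 − p). Take p = 0.20 in controls and a true OR of 2, so p = 0.40/1.20 = 0.333 in cases. At Se 0.80 and Sp 0.95, q is 0.30 in cases and 0.20 in controls, so the observed OR is (0.30/0.70)/(0.20/0.80) = 1.71.

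| Se / Sp | True OR 2 | True OR 3 |
|---|---|---|
| 0.80 / 0.95 | 1.71 | 2.36 |
| 0.50 / 0.90 | 1.39 | 1.70 |
| 0.50 / 0.80 | 1.22 | 1.39 |

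Across control prevalences of 5%, 20% and 40%, the observed value runs from 1.08 to 1.71 for a true OR of 2, and from 1.16 to 2.36 for a true OR of 3. The protocol gives no Se or Sp. The table shows direction only, for error that is equal in cases and controls. Error made unequal by the skips need not stay within this range. Prescribed laxatives remain in the database records, so only the over-the-counter part is exposed to this error.

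**The case against.** The form is mainly an instrument for validating diagnoses. Section 9.3.4 gives its targets as IBS-C and SCD, and questions 2 to 4 stand under a diagnosis-confirmation heading, where treatment at the IBS-C date is a sensible corroborating item. Section 9.9 is a limitations section. It gives no rule for dating over-the-counter answers and already concedes that laxative use will be incompletely captured. The current-user definition requires a prescription or dispensation, which over-the-counter use would not meet. The coding rule may sit in an analysis plan that is not shown. Question 7 is free text, so a GP could name a drug started later.

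Much of this stands, and it limits the point. It is a reason to keep the IBS-C-date question. It does not remove the conflict: Section 9.9 says the answers will be included, and the only dated treatment answers on the form carry the wrong date for that use.

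A reader might go further in three ways that the protocol does not support:

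- **Both main exposures are misclassified.** Linaclotide status comes from prescription records, so its classification is not changed.
- **Most answers are wrong.** If index dates were spread evenly over 2, 3 or 5 years after the IBS-C date, only 90/(365.25 × years) = 12%, 8% or 5% would fall within 90 days of it. That measures an assumed date gap. A patient who keeps taking a laxative is a current user at any gap, so the remainder is not a misclassification rate.
- **Prevalent patients could never have linaclotide reported.** This holds only if the undefined date is a first record before launch. UK cohort entry is never before 13 May 2013.

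**Conclusion.** The mismatch is plain in the text. Treatments are elicited at an undefined IBS-C event date, exposure is classified at the index date, and Section 9.9 plans to use the over-the-counter laxative answers. The consequence falls on laxative exposure among UK responders, with collection that can differ between cases and controls through the skips after questions 1 and 5.

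For linaclotide the loss is smaller. The form cannot confirm use at the index date, and questions 6 and 7 are not worded to capture the response to stopping a drug that was started after the IBS-C event date.

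The gap between the dates can reach about 10.5 years in the UK if the IBS-C event date is cohort entry. For patients whose two dates lie close together the problem is small. Without the distribution of the gap, or any sensitivity and specificity, its overall size cannot be given.

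**What to change.** 1. **Define the IBS-C event date** in the protocol and on the form.
2. **Reconcile the exposure windows** in Section 9.3.2 (90 days after supply ends, against a prescription in the prior 45 days) before fixing any look-back for this purpose.
3. **Forms already returned.** State that answers to questions 2 to 4 do not define index-date exposure and do not add over-the-counter laxatives unless the date they refer to falls within the look-back before the index date. Report this as a limitation in Section 9.9. UK validation was scheduled for Q2-Q3 2024 (Table 1) and the current version dates from October 2024, so this rule is the main remedy.
4. **Forms still to be sent, if any.** Keep the IBS-C-date question if it is wanted for confirming the diagnosis. Add a treatment item, naming over-the-counter laxatives, for the diarrhoea or index date and its look-back. Ask it of cases and controls alike, whatever the answers to questions 1 and 5, and point questions 6 and 7 to that list.

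The cost is one definition, one analysis rule and, at most, one added question. Some over-the-counter laxative information is discarded, including some from patients who were in fact still using the laxative at the index date.
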